### 10.2. Populations for Analyses

For purposes of analysis, the following populations are defined:

Population	Description
Enrolled	All participants who sign informed consent form
Full Analysis Set (FAS)	All enrolled participants who take at least 1 dose of study treatment
Safety	Identical to FAS, as no randomization occurs (single arm trial)
Per Protocol Set (PPS)	All FAS subjects, who also meet the following criteria: a) have no violations of inclusion/exclusion criteria b) have not discontinued from the study prior to 24 weeks c) have not been off study medication for more than 14 consecutive days during the treatment period d) have not received chronic (lasting longer than 14 consecutive days) systemic glucocorticoid therapy (excluding topical, intra-articular, intra-ocular, and inhaled preparations)

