- All vital signs should be recorded in the subject in a resting state. If there is a suspicion of postural hypotension or autonomic instability, the investigators at their discretion might decide to record the blood pressure in a supine state and then after standing for 2 minutes to detect any postural hypotension. Blood pressure measurements should be done in the left arm with sphygmomanometer held at the level of the heart. Blood pressure recording in both arms is at the investigators' discretion in selective cases of pulse volume inequality or pulse being absent in either of the arms.
- Subjects will be instructed to daily measure the FBG levels mandatorily using glucometer before the morning meal till Week 12 and record in the subject diary. Also, subjects will be instructed to measure and record the blood glucose levels using glucometer if they have symptoms of hypoglycemia (including nocturnal hypoglycemia) at any time of the day or night.
- 1. Subjects will be instructed to perform 7-point SMBG level monitoring (glucose measurements before breakfast, lunch, and dinner; 2 hours after breakfast, lunch, and dinner; and at 3 am [± 1 hour]) 2-3 days in the week prior to Visits 2, 3, 4, 5, and 8, and record the values in the subject diary. Subjects will be instructed to carry the glucometers to the sites on Visits 3, 4, 5, and 8.
- . Subjects will be instructed to record the actual time and dose of Basaglar administration in the subject diary.

5. Changes/deviations from the planned analysis

Any deviation in implementing original statistical plan will be described and justified in the final clinical study report.

6. Analysis populations

Agreement and authorization of participants included/excluded from each analysis population will be reached prior to final database hard lock. Sponsor will supply a list of all participants to be excluded from the relevant analysis populations, including the reason(s) for exclusion from the analysis populations.

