6.3 Per-Protocol Analysis Set (PPS)

This analysis population will include all FAS subjects, who also meet the following criteria:

- a) Have no violations of inclusion/exclusion criteria
- b) Have not discontinued from the study prior to 24 weeks
- c) Have not been off study medication for more than 14 consecutive days during the treatment period
- d) Have not received chronic (lasting longer than 14 consecutive days) systemic glucocorticoid therapy (excluding topical, intra-articular, intra-ocular, and inhaled preparations)
 - Set to 'Y' if
 1. For all FAS subjects = "Y" and

- Date of completion/discontinuation is not less than date of visit 8 (week 24)
- 3. within a subject there is no DV.DVCAT = "MAJOR"

CONFIDENTIAL CS.BS.01.00 TPL-1.0: Statistical Analysis Plan Template

Page 19 of 85

7. General considerations

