12.2 Analysis

| Population: | FAS and PPS populations |
|-----------------|---|
| Stratification: | Table: NA |
| | Listing: By Subject |
| Statistics: | Listing will be provided for daily dosing treatment exposure data for |
| | each subject. |

13. IMP compliance

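### The SAP 6.3 per-protocol flag does not implement the per-protocol set that the protocol and the SAP text define

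*SAP*

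**What the plan says.** SAP 6.3 first repeats the list in protocol 10.2. A PPS subject is an FAS subject who satisfies:

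- (a) "Have no violations of inclusion/exclusion criteria"
- (b) no discontinuation before 24 weeks
- (c) "Have not been off study medication for more than 14 consecutive days during the treatment period"
- (d) no systemic glucocorticoid course running beyond 14 days in a row, with topical, intra-articular, intra-ocular and inhaled routes excepted

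The programming rule printed beneath it sets the flag to Y on three conditions: the subject is in the FAS; "Date of completion/discontinuation is not less than date of visit 8 (week 24"); and "within a subject there is no DV.DVCAT = 'MAJOR".

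Other parts of the plan bear on the same set:

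- Protocol 7.4 says that subjects who needed rescue medication are left out of the PPS.
- Protocol 7.6 treats a subject who misses more than 3 consecutive days, or more than 15 days in total, as withdrawn.
- SAP section 6 requires membership to be agreed before final hard lock and adds: "Sponsor will supply a list of all participants to be excluded from the relevant analysis populations".
- Protocol 7.3 describes the study as open-label.
- SAP 19.2.1 names both FAS and PPS for the primary analysis, and protocol 10.3.2.1 repeats every hypoglycemia analysis on the PPS.

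**The concern.** The definition and the flag are different rules, and the SAP does not say which governs. The definition is objective: each criterion can be checked against a date, a dose record or a medication record. The flag passes three of the four criteria to a deviation grade whose meaning the available text does not give. Whoever assigns the grade decides who is in the set.

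Two things are at stake. The first is fidelity: the PPS in the report may not be the one the protocol describes, and the rescue exclusion may not be applied at all. The second is independence from outcome. The PPS is the only alternative population in which the primary incidence is examined. With no blinding, and no stated date for the deviation grading, the plan has no safeguard against grading with a subject's hypoglycemia or HbA1c results in view.

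**Working it through.** **Step 1: set each exclusion against the flag.**

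| Exclusion | Source | Named in the flag? |
|---|---|---|
| (a) any entry-criterion violation | Protocol 10.2, SAP 6.3 | No; only if graded MAJOR |
| (b) discontinued before 24 weeks | Protocol 10.2, SAP 6.3 | Yes, condition 2 |
| (c) off drug more than 14 consecutive days | Protocol 10.2, SAP 6.3 | No; only if graded MAJOR |
| (d) systemic glucocorticoid more than 14 consecutive days | Protocol 10.2, SAP 6.3 | No; only if graded MAJOR |
| Rescue medication | Protocol 7.4 | No; only if graded MAJOR |

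**Step 2: look for a definition of MAJOR.** The SAP body, from section 1.1 to Appendix 2, gives none and cites no deviation plan. The protocol has no major-deviation criterion. Criterion (a) carries no severity grade, so an entry violation graded below MAJOR fails the definition and passes the flag. The SAP derives no 14-day gap anywhere; its compliance rules in section 13.1 use 3 and 15.

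**Step 3: errors the flag permits.** It can remove a subject who meets every stated criterion but has some other deviation graded MAJOR. It can keep a subject with an entry violation, a gap over 14 days, a long glucocorticoid course or rescue use that was not graded MAJOR.

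**Step 4: the plan's own figures.** The documents give no expected PPS size and no deviation rate. The nearest figures reproduce:

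- Screened: 250 / 0.85 = 294.1, rounded up to 295.
- Completers: 250 × 0.80 = 200.
- Table ABEX.3 at n = 200, p ± 1.96 × sqrt(p(1 − p)/n): 6.7% to 15.3% at 11%, and 23.6% to 36.4% at 30%.

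**Step 5: illustration.** Assume a correct PPS of 200 (the completer target), with x = 22 events (11%) or x = 60 (30%), and k subjects misclassified. If k are wrongly removed, the estimate lies between (x − k)/(200 − k), when all had an event, and x/(200 − k), when none had. If k are wrongly kept, it lies between x/(200 + k) and (x + k)/(200 + k).

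| | 11% (22/200) | 30% (60/200) |
|---|---|---|
| Clopper-Pearson 95% CI, no error | 7.0% to 16.2% | 23.7% to 36.9% |
| 5 removed | 17/195 = 8.7% to 22/195 = 11.3% | 55/195 = 28.2% to 60/195 = 30.8% |
| 10 removed | 12/190 = 6.3% to 22/190 = 11.6% | 50/190 = 26.3% to 60/190 = 31.6% |
| 10 wrongly kept | 22/210 = 10.5% to 32/210 = 15.2% | 60/210 = 28.6% to 70/210 = 33.3% |

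These are extremes. If misclassification is unrelated to outcome, the expected incidence does not move. The cost of losing 10 subjects is then precision only: the interval widens by about sqrt(200/190) = 1.026, or 3%.

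**The case against.** The strongest reply is that criteria (a) to (d) remain in SAP 6.3 as the definition, and the flag is only shorthand for programmers. A deviation plan outside these documents could map MAJOR exactly to the criteria, and the SAP pages before section 1.1 were not all available to this review. No passage grades a consent or visit deviation as MAJOR, or a 15-day gap as minor. This stands to the extent that misclassification is possible but not shown. It does not rescue the text, because the SAP cites no such plan and nothing in its body ties the grade to the criteria.

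A reader might infer that protocol 10.2 is a closed list, so that any further exclusion breaches the protocol. Protocol 7.4 shows otherwise. For the same reason, simply dropping the MAJOR condition and testing (a), (c) and (d) would be wrong: rescue users would stay in the PPS.

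A reader might also infer that deviations are graded after outcomes are seen. The documents do not date the grading, and they require membership to be agreed, with reasons, before hard lock. What can be said is that an open-label design with no stated date for the grading does not prevent it.

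Protocol 7.6 partly covers long gaps, since such a subject counts as withdrawn and so may fail (b). That works only if the recorded end date falls before Visit 8, and it leaves (c) with an unclear role.

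Finally, no decision rests on the PPS. Protocol 10.3.1 places the analyses on the FAS, the primary result is a single-arm proportion with an interval, and SAP 7.4 plans no comparison tests. This limits the weight of the point.

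**Conclusion.** The point holds: the flag in SAP 6.3 is not the PPS that the protocol and the SAP text define. Three criteria depend on an undefined deviation grade, and the rescue exclusion of protocol 7.4 is not carried into protocol 10.2, the SAP list or the flag. The documents do not support the stronger reading that subjects will be misclassified, or that grading will follow the results.

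No size follows from the documents. The illustrative bounds (6.3% to 11.6% for 10 removals at 22/200) rest on an assumed PPS of 200, an assumed number of errors and the most extreme selection. The FAS estimate is unchanged, because SAP 6.2 makes FAS membership depend on dosing alone. This should be corrected because the primary analysis is also run on the PPS; it does not threaten the main result.

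**What to change.** Replace condition 3 of the flag with tests on recorded data:

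1. No recorded inclusion or exclusion violation, whatever its grade.
2. Longest gap in the daily dosing records of 14 days or less. Protocol 7.2.1 sends all administrations to the eCRF, and SAP 12.2 lists "daily dosing treatment exposure data". SAP 13.1 describes only counts and a yes/no item on missed doses by visit, so confirm that the daily records are in the database.
3. No systemic glucocorticoid record over 14 consecutive days, with the listed routes excluded. SAP 15.1 holds ATC codes, route and dates.
4. No rescue-medication record, in line with protocol 7.4. SAP 15.1 already identifies the first rescue date.

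Alternatively, keep condition 3 but define MAJOR, for PPS purposes, as exactly these criteria in a dated document fixed before outcome data are reviewed.

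Under either option, add rescue use to the PPS list in SAP 6.3 and limit the sponsor's list to reproducing the rule. Protocol 7.6 must also be reconciled with criteria (b) and (c), so that it is clear how a subject with missed doses is classified.

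The cost is SAP wording and modest programming on data the plan already collects. Subjects with other major deviations stay in the PPS and are shown in a listing.

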7.1 Visit and date conventions

Visit day will be calculated from the reference start date which will be used to present start/stop day of assessments and events. The *reference start date* is defined as the date of first IMP administration. The following conventions will be used for event references:

Date of event less than reference treatment start date

• Event day = date of event - reference treatment start date

[figure not shown]
Date of event greater than equal to reference treatment start date

• Event day = date of event - reference treatment start date + 1

Above two formulae will be use for the calculation of the duration (in days) for the respective events (i.e. AEs etc).

Visit windowing (i.e. remapping of visits based on visit windows) will be performed for this trial. The assigned nominal visit will be used for by-visit summaries. In the situation where the assessment/event date is partial or missing, visit day/week, and any corresponding durations will appear missing in the data listings. Unscheduled measurements will not be included in by-visit summaries. Data listings will include scheduled, unscheduled, and early discontinuation data. The following figure 7.1 illustrates the study design.

Figure 7.1

*Telephone visit

Abbreviations: GLP-1 RA = glucagon-like peptide-1 receptor agonist; OAM = oral antihyperglycemic medications; QD = once daily.

The study design includes the following periods:

- Screening (Week -2 to Week 0)
- Treatment period
 - Titration period (Week 0 to Week 12)
 - Maintenance period (Week 12 to 24)
- Safety Follow-up (Week 28)

Trial visit will be assigned as delineated in Table 7.1:

| | Screen | | | Follow-up | | | | | | |
|-----------------------------------|----------|---|----|-----------|----|-----|-----|-----|-------|--|
| Visit Day | -14 to 0 | 0 | 28 | 56 | 84 | 112 | 140 | 168 | 196 | |
| Visit Week | -2 | 0 | 4 | 8 | 12 | 16 | 20 | 24 | 28 | |
| Visit No. | 1 | 2 | 3 | 4 | 5 | 6 | 7 | 8 | 9 /ET | |
| Allowable Deviation +/- (days) | | 3 | 7 | 7 | 7 | 7 | 7 | 7 | | |

The below detail mentioned procedures will be completed at each visit:

Screening period (Week -2 to Week 0) i.e. Visit 1

The following procedures will be completed for each study participant:

- Informed consent
- Inclusion / Exclusion Criteria
- Demographic information
- HIV and Hepatitis testing
- Physical Examination
- Vital Signs
- Medical History and family history of CV disease
- History of substance usage
- 12-lead ECG
- Laboratory Sample Collection
- Trainings on injection technique, use of glucometer and 7-point SMBG measurement
- Dispense study diary
- Dispense glucometer
- Concomitant medication review

Treatment period (Week 0 to Week 24) i.e. Visit 2, 3, 4, 5, 6, 7 and 8

Study participants found eligible during the screening period will begin their treatment at Visit 2. All measures to be performed at Visit 2 will be done prior to administration of Basaglar. At these visits, participants will undergo the following procedures and evaluations.

- Vital Signs (for visit 2,3,4,5, 8 and 9 only)
- Concomitant medication review
- Dispense study diary (for visit 2 only) Hypoglycemia Events Summary
- FBG (for visit 2,3 and 4 only)
- Adverse events and Serious adverse events
- Blood Glucose Monitoring (7-point reading) (for visit 2,3,4,5 and 8 only)
- Treatment exposure
- Urine Pregnancy Test (for visit 2)
- HbA1c measurement (for visit 2,5 and 8)
- Insulin Treatment Satisfaction Questionnaire (ITSQ) (for visit 3 and 8)
- Hematology, clinical chemistry, and urinalysis tests (for visit 5 and 8)

- Hepatic Monitoring Tests
- Trainings on signs/symptoms of hypo/hyperglycemia and insulin reactions
- Trainings on injection technique, use of glucometer and 7-point SMBG measurement (for visit 2,3,4,5 and 8 only)
- Self-titration training
- Dispense study drug (for visit 2,3,4 and 5 only)
- Review study diary (for visit 2,3,45 and 5 only)
- Substance use Alcohol (Initial/Historical)
- Substance use Recreational Drug (Initial/Historical)

Follow-up Visit (Week 28) i.e. Visit 9

- Vital Signs
- Concomitant medication review
- Adverse events and Serious adverse events
- Hypoglycemia Events Summary
- Completion or discontinuation of investigation

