8.2 Missing data

- Vital Signs: we will use the last observation carry forward (LOCF) method for the missing values.
- 2) Actual and Change from Baseline HbA1c: For subjects requiring rescue medication, HbA1c values recorded after the first administration of rescue medication will not be considered for analysis, and these values will be considered as missing. In addition, for the actual value and change from baseline, a descriptive analysis using LOCF will be performed, using the baseline or 12-week value, if the 24-week value is missing or occurred after use of rescue medication.
- 3) Subjects Reaching HbA1c Targets (≤6.5% and <7%) at Week 24: The HbA1c values used to calculate this binary variable will be the LOCF value, that is, in case the Week 24 value is missing, the Week 12 value will be used. The denominator will be the total FAS population. Subject with missing HbA1c data at Week 12 and Week 24 will be considered as not having reached the target.

For other efficacy parameters 7-point SMBG levels (mg/dL and mmol/L), body mass index (kg/m²), body weight (kg), basal insulin dose (U/day and U/kg/day) we will apply the LOCF method for missing data.

4) ITSQ score: If an item score is missing for a subject and ≤20% of the items within the domain (or overall) are missing for that subject, then the mean of the items scores in the domain (or overall) will be imputed for the missing item score(s). If there are >20% missing items, the individual subject domain (or overall) score will be set to missing. that is here we will use the mean imputation method.

Page 25 of 85

Change at Week 24 from Week 4 for ITSQ score (Transformed overall and domain scores): we will use the last observation carry forward (LOCF) method for the missing values.

5) Laboratory data: we will use the last observation carry forward (LOCF) method for the missing values.

For all other cases the missing data will not be imputed for this trial.

9. Output presentations

This is single arm study; we are not doing any stratification we will present the summary table for single treatment group i.e. Basaglar.

The Section 23, Appendix 1 describe the format and content for presentation of tables, listings and figures (TLFs).

All percentages (%) for a specific summary are calculated using the total number of participants included in the relevant analysis population as the denominator, unless otherwise specified.

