15.2 Analysis

| Population: | FAS and PPS |
|-----------------|--|
| Stratification: | Table: by ATC and PT |
| | Listing: By subject |
| Statistics: | Concomitant medication and Special Interest |
| | Hyperglycaemia related concomitant medication will be |
| | summarized separately as (frequency, percentages) for |
| | table and listing will be presented for concomitant |
| | medication and Special Interest Hyperglycaemia related |
| | concomitant medication. |
| | The rescue medication will be summarized as (frequency |
| | and percentage) by visit (i.e. Week 4, 8, 12, 16, 20 and 24) |
| | for FAS population. |
| | By using formula mentioned in derivation section for rescue |
| | medication, we will get the Day at which the rescue |
| | medication will be started per subject, then we will convert |
| | these days to respective visits. |

e.g. if, subject in the trial who needs rescue medication on day 30 (Day 30 is calculated using derivation mentioned above for rescue medication) then this subject will be counted under week 4 visit (as Day 30 comes under the week 0 to week 4 visit).

Denominators for "n" are per visit, for "n-cumulative" it will be the number of subjects with at least 1 visit up to respective visit.

16. Adverse events

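### SAP Table 7.1 uses scheduling tolerances as analysis windows on a different day count from the SAP's own formula, so some permitted visits, including Week 24, map to no visit, and no rule covers them

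*SAP*

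**What the plan says.** SAP 7.1 says "Visit windowing (i.e. remapping of visits based on visit windows) will be performed for this trial" and "Trial visit will be assigned as delineated in Table 7.1". By-visit summaries then use the assigned visit, and unscheduled measurements are left out of them.

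Table 7.1 has two working rows: "Visit Day | -14 to 0 | 0 | 28 | 56 | 84 | 112 | 140 | 168 | 196" and "Allowable Deviation +/- (days) | | 3 | 7 | 7 | 7 | 7 | 7 | 7". The second repeats the tolerances in the protocol's Schedule of Activities (Section 2). Visits 1 and 9/ET are blank in both documents.

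The same SAP section sets the reference date, which "is defined as the date of first IMP administration", and for dates on or after it gives "Event day = date of event - reference treatment start date + 1". The first-dose date is therefore Day 1, and there is no Day 0.

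For HbA1c, SAP 8.2 fills a missing Week 24 value by LOCF, "using the baseline or 12-week value, if the 24-week value is missing or occurred after use of rescue medication". LOCF is also planned for weight, BMI, vital signs, laboratory data and ITSQ scores. SAP 15.2 counts rescue starts by visit and places a Day 30 start under Week 4, "as Day 30 comes under the week 0 to week 4 visit".

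**The concern.** A scheduling tolerance tells a site when a visit is on time. An analysis window has to give every usable measurement exactly one visit. Table 7.1 is asked to do the second job with numbers made for the first, and its day origin differs from that of the formula printed beside it. The SAP has no rule for a value in no window, a value in two windows, or two values in one window.

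What is at stake is the Week 24 secondary data. Post-baseline HbA1c and laboratory samples are scheduled only at Weeks 12 and 24, weight at Visits 1, 2 and 8, and ITSQ at Weeks 4 and 24. If a measured Week 24 value has no assigned visit and is treated as missing, LOCF substitutes an older one. For weight that is normally the Visit 2 value, and for ITSQ the Week 4 value, so a measured change becomes zero. Two programmers could also build different Week 24 datasets from the same text.

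**Working it through.** **Inputs.** Target days and tolerances: SAP Table 7.1. Day formula and reference date: SAP 7.1. Dosing from Visit 2: protocol 5.1. Follow-up four weeks after the last dose: protocol 5.1.1.

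**The table's own figures.** Target = 7 × week gives 0, 28, 56, 84, 112, 140, 168, 196, which reproduces all eight printed targets. The SAP formula adds 1, so an on-time Week 24 visit is Day 169 and an on-time Week 28 visit is Day 197.

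**Windows (target ± tolerance) and gaps.**

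| Visit | Window | Gap to next window |
|---|---|---|
| 2 | -3 to 3 | 4-20 (17 days) |
| 3 | 21-35 | 36-48 (13) |
| 4 | 49-63 | 64-76 (13) |
| 5 | 77-91 | 92-104 (13) |
| 6 | 105-119 | 120-132 (13) |
| 7 | 133-147 | 148-160 (13) |
| 8 | 161-175 | 176-195 (20) |
| 9/ET | 196 only | none |

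**Off by one.** Assume first dose on the Visit 2 date and visits counted from it. Visit 8 is permitted 161 to 175 days later, which is Days 162 to 176. The last date, 175 + 1 = 176, exceeds 175, so 1 of 15 permitted dates is unassigned. The +7 dates of Visits 3-7 fall on Days 36, 64, 92, 120 and 148, also just outside.

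**Sensitivity to the anchor.** The protocol does not state the date from which tolerances run.
- If the first dose is the day after Visit 2, the +7 date is Day 175 and stays inside.
- If all visits are anchored to the planned schedule from screening, let Visit 2 be s days off plan (-3 to 3) and Visit 8 d days off (-7 to 7). Visit 8 is then Day 169 + d - s, unassigned when d - s is at least 7 or at most -9. For s = -3 to 3 this removes 4, 3, 2, 1, 0, 1 and 2 dates: 13 of 7 × 15 = 105 combinations.

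**Visit 9.** If follow-up is 28 days after Visit 8, and Visit 8 is 161 to 175 days after first dose, follow-up falls on Days 190 to 204. Only one of these 15 dates is Day 196 (167 + 28 + 1).

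**Screening.** The printed range of -14 to 0 overlaps Visit 2 on Days -3 to 0 (-3 to -1 on the SAP's count). If Visit 2 is 1, 2 or 3 days late, as permitted, Visit 1 is Day -15, -16 or -17, before the range starts.

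**Rescue.** Day 30 lies inside the table's Week 4 window (21-35) but after Day 28, so the example agrees with the table and not with the interval given as its reason. A rescue start on Day 40 lies in the 36-48 gap and has no visit under the table.

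**The case against.** The strongest reply is that nothing need be lost. The SAP never says that out-of-window values are discarded; the only stated exclusion is of unscheduled measurements. The assigned nominal visit can be read as the eCRF visit, the table row is labelled as an allowable deviation, and several derivations name visits directly (the dates of Visits 2 and 8, the Week 24 HbA1c collection date). On that reading every value keeps its visit. This stands as a possible reading, but it sits badly beside an explicit statement that visits are remapped and assigned by the table. The SAP should say which applies.

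The off-by-one effect is also narrow: one permitted date per visit, under a stated anchor. Most gap dates are protocol deviations in any case. Both points stand and limit the size.

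Three stronger inferences are not supported:
- A reader might infer that late screening visits lose their laboratory baselines. SAP 7.2 and 17.1 take the last pre-dose value without a window, and screening is the only scheduled pre-dose laboratory sample, so those baselines are largely protected. What remains is the Week -2 label in by-visit rows and in the laboratory model of SAP 17.2.
- A reader might infer that the Day 30 rescue example contradicts Table 7.1. It does not; only its stated reason fails.
- A reader might take the 13 uncovered days in each 28 (46%) as the share of data at risk. That is calendar coverage. Visits cluster around their targets.

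**Conclusion.** The point holds as a fault in a stated rule. Table 7.1 is not contiguous, overlaps at screening and Visit 2, gives Visit 9/ET a single target day, and uses a different day origin from the formula beside it. With first dose on the Visit 2 date and visits counted from it, a fully compliant Visit 8 on its last permitted date is Day 176 and has no visit.

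The consequence is conditional. If the table is applied literally, Week 24 HbA1c, weight, laboratory, vital-sign and ITSQ values from such a visit would be treated as missing and replaced by LOCF. The SAP does not state this. The number of subjects affected cannot be computed: the documents give no rate of late visits, so any count out of the 200 planned completers would rest on an assumed rate.

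The primary hypoglycemia endpoint (SAP 19.1.1) uses the recorded Visit 2 and Visit 8 dates and is affected only if Visit 8 itself is left unassigned. The matter should be corrected, but it does not threaten the main result.

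**What to change.** Preferred: summarise scheduled assessments by the eCRF visit and use Table 7.1 only to flag timing deviations.

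Alternative: define contiguous windows on the Day 1 count, with targets 29, 57, 85, 113, 141, 169 and 197. Put cut-offs midway between the visits at which each variable is measured, state lower and upper bounds, and take the value closest to target. For HbA1c and laboratory data the cut between Weeks 12 and 24 is (85 + 169)/2 = 127. Bounds at the midpoints to the neighbouring scheduled visits, (57 + 85)/2 = 71 and (169 + 197)/2 = 183, would give Week 12 as Days 71-126 and Week 24 as Days 127-182.

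Under either option:
- Take the last pre-dose value as the laboratory (Week -2) baseline, whatever its day.
- State one contiguous interval rule for tabulating rescue by visit, for example Days 1-28 as Week 4 and Days 29-56 as Week 8, and correct the Day 30 example to match.

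The cost is SAP wording and programming, with no change to the protocol or data collection. The downside is that some early or late values are summarised with on-time ones. Under the wide HbA1c window, a Day 127 value (126 days, or 18 weeks, after first dose) would count as Week 24, so the bounds should be chosen deliberately.
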